12.5. Appendix 5: Origin of Data/Samples

The following table of study objectives specifies, for each objective, the provenance of clinical data and samples which will be used to explore that endpoint

Objective	Endpoint	Origin of Data/Samples
Co-Primary		
1. To determine the impact of thermal injury on the magnitude of small intestinal permeability change as soon as possible following injury compared to healthy participants	
 Lactulose/Mannitol (L/M) ratio at entry 	
 HESTIA study
2. To characterise the effect of thermal injury on small intestinal permeability over time and establish the clinical and demographic factors which can influence it	
 Changes in L/M ratio over time 	
 HESTIA Study
Exploratory		
3. To determine the impact of thermal injury on colonic permeability as soon as possible following injury compared to healthy participants	
 Fractional excretion of sucralose at entry 	
 HESTIA Study
4. To characterise the effect of thermal injury on colonic permeability over time	
 Changes in the fractional excretion of sucralose over time 	
 HESTIA Study
5. To assess the relationship between severity of a participant's condition following thermal injury and changes in intestinal permeability†	
 Number of ventilator-free days Number of vasopressor-free days Number of hemofiltration-free days Number of episodes 	
 All clinical data will be obtained from SIFT12. Permeability measurements will be obtained from HESTIA

Objective	Endpoint	Origin of Data/Samples
	
of confirmed infection and sepsis
 
 • Number of surgical interventions • Total length of hospital stay • Calculate critical care and thermal injury severity scores 	

6. To assess plasma and urine biomarkers of intestinal permeability, bacterial translocation and renal tubular dysfunction following thermal injury†
	
 • Change in markers of intestinal mucosal damage samples from blood • Change in urine protein:creatinine and urine albumin:creatinine ratios 	
 • Blood biomarkers obtained from SIFTI-2 (and HESTIA for healthy participants) • Urine for microbial metabolite analysis, claudin 3 and KIM 1 obtained from SIFTI-2 (and HESTIA for Healthy participants) • Urine albumin:creatinine and protein:creatinine ratios obtained from SIFTI-2 (and HESTIA for healthy participants) • Permeability data (STM absorption) from HESTIA

7. To assess the impact of thermal injury and intestinal permeability on the intestinal microbiome compared to healthy participants
	
 • Changes in microbiome of acute and convalescent stool samples 	
 • Stool samples collected in HESTIA protocol • Permeability data from HESTIA

8. To assess the impact of pre-existing co-morbid conditions on intestinal permeability and clinical outcome following thermal injury†
	
 • Medical history and drug history at the time of admission 	
 • Medical History data from HESTIA • Permeability data from HESTIA

9. To assess wound healing
	
 • Time to wound recovery (e.g. 95%) 	
 • Wound healing assessment data from clinical notes will be captured in HESTIA at 14

Objective	Endpoint	Origin of Data/Samples
		day, 28 day and 6 month visits.
10. To characterise intestinal microbiota, and correlate its composition with both intestinal permeability and bacterial detection in blood†	
• Changes in intestinal microbiome• Bacterial markers of translocation	
• Microbiome data from HESTIA study• Blood Biomarker data from SIFTI-2 (thermally injured participants) and HESTIA (healthy participants).

12.6. Appendix 6: Protocol Amendment History

The Protocol Amendment Summary of Changes Table for the current amendment is located directly before the Table of Contents (TOC).

Amendment 01 (15-Aug-2017)

Overall Rationale for the Amendment: The interim analysis has been removed since lactulose and mannitol data in healthy controls was unlikely to change the required sample size in thermally injured participants.

Section # and Name	Description of Change	Brief Rationale
10.5.3 Interim Analysis	Removed preliminary review of lactulose/mannitol ratio data.	Analysis of lactulose and mannitol data in healthy controls would be unlikely to change the study size, and will no longer be performed.
5.2 Number of Participants	Included withdrawn participants may be replaced.	To ensure the target number of evaluable population is maintained.
5.4.4 Preliminary Data Review	Modified the preliminary data review.	To describe the change in preliminary data review.
Synopsis	Updated preliminary data review.	For consistency.
6.5 Exclusion Criteria	Revision to eligibility criteria to exclude hepatitis infection for thermally injured participants. Addition the personal consultee will not be notified if a patient lacking mental capacity was found to be HIV positive.	Consistency correction. Hepatitis screening will be performed. To provide Ethic Committee reassurance and address any ambiguity of this information.
8.2.1 Other Withdraw Criteria	Added the withdraw of participants receiving hemodialysis.	Renal replacement therapy (i.e. dialysis) may filter out lactulose and mannitol.
9.2.2 Time Period and Frequency for Collecting AE and SAE Information	Added: Any SAEs assessed as related to study participation will be recorded from the time a participant consents. All SAEs will be recorded and reported to the sponsor or designee immediately and under no	To align with the updates to Clinical Protocol Template (Vol 7) effective 7th April 2017.

Section # and Name	Description of Change	Brief Rationale
	circumstance should this exceed 24 hours.	
9.4 Clinical Safety Laboratory Assessments	Removal of if laboratory values from non-protocol specified laboratory assessments performed at the institution's local laboratory.	To align with the updates to Clinical Protocol Template (Vol 7) effective 7th April 2017.
Appendix 4: Adverse Events: Definitions and Procedures for Recording, Evaluating, Follow-up, and Reporting	Reporting SAE to GSK if the electronic system is unavailable.	To align with the updates to Clinical Protocol Template (Vol 7) effective 7th April 2017.

DOCUMENT HISTORY	
Document	Date
Amendment 2	26-Sep-2017
Amendment 1	15-Aug-2017
Original Protocol	02-Mar-2017

1. SUMMARY OF KEY PROTOCOL INFORMATION

1.1. Changes to the Protocol Defined Statistical Analysis Plan

This study was terminated prior to the full sample size being achieved. As a result the initially planned sample size of 25 for the thermally injured subjects is greatly reduced to 3. Changes from the originally planned statistical analysis specified in the protocol (Dated:26SEP2017) are outlined in Table 1.

Table 1 Changes to Protocol Defined Analysis Plan

Pro	Protocol		Reporting & Analysis Plan				
Sta	tistical Analysis Plan		Statistical Analysis Plan		Rationale for Changes		
•	Co -Primary Objective 1: To determine the impact of thermal injury on the magnitude of small intestinal permeability change as soon as possible following injury compared to healthy participants.	•	Summary statistics for Lactulose/Mannitol (L/M) ratio at entry will be provided. No formal stats analysis for comparing the groups.	•	No stats analysis due to limited sample size.		
•	Exploratory objective 1: Comparison of Fractional excretion of sucralose of TI participants with Healthy participants at baseline	•	Only summary will be provided. No formal stats analysis for comparing the groups.	•	No stats analysis due to limited sample size.		
•	 Exploratory objective 3: Number of ventilator-free days, vasopressor-free days, hemofiltration-free days, episodes of confirmed infection and sepsis, surgical interventions Total length of hospital stay Calculate critical care and thermal injury severity scores 	•	None of the endpoints will be analysed for final reporting.		 Due to limited sample size, these endpoints will not be analysed. Where relevant, these will be described using data from the SIFTI2 CRF in CSR. 		
•	Exploratory objective 4: Change in urine protein: creatinine and urine albumin: creatinine ratios	•	This endpoint will not be analysed.	•	The reason for collecting these data was to inform a pharmacokinetic model. As development of the molecule has been terminated, this model is no longer required, moreover data collected are so limited that analysis is not possible.		
•	Exploratory objective 5: Changes in microbiome of acute and convalescent stool samples	•	This endpoint is not considered for final analysis.	•	Only one stool sample has been collected from a TI patient thus no meaningful comparison is possible.		
•	Exploratory objective 7: Time to wound recovery	•	This endpoint will not be analysis but will be listed.	•	Sufficient data not available to perform the analysis.		
•	Exploratory objective 8: • Determine fluid input/output balance	•	These endpoints are not considered for final	•	Sufficient data not available to perform the analysis.		

Protocol	Reporting & Analysis Plan			
Statistical Analysis Plan	Statistical Analysis Plan	Rationale for Changes		
over time • Changes in serum albumin and plasma creatinine	analysis.			
 Exploratory objective 9: Changes in intestinal microbiome Bacterial markers of translocation 	 No microbiome data analysis Bacterial markers of translocation will be summarised. 	Insufficient stool samples have been collected for correlative analyses in TI participants.		

1.2. Study Objective(s) and Endpoint(s)

1.2.1. Protocol Defined Objectives and Endpoints

[figure not shown]
Objectives	Endpoints		
Primary Objectives	Primary Endpoints		
To determine the impact of thermal injury on the magnitude of small intestinal permeability change as soon as possible following injury compared to health participants			
To characterise the effect of thermal injury on small intestinal permeability over time and establish the clinical and demographic factors which can influence it			
Exploratory Objectives	Exploratory Endpoints		
To determine the impact of thermal injury on colonic permeability as soon as possible following injury compared to healthy participants	Fractional excretion of sucralose at entry		
To characterise the effect of thermal injury on coloni permeability over time	Changes in the fractional excretion of sucralose over time		
To assess the relationship between severity of a participant's condition following thermal injury and	Number of ventilator-free days		
changes in intestinal permeability	Number of vasopressor-free days		
	Number of hemofiltration-free days		
	 Number of episodes of confirmed infection and sepsis 		
	 Number of surgical interventions 		
	Total length of hospital stay		
	 Calculate critical care and thermal injury severity scores 		
To assess plasma and urine biomarkers of intestinal permeability, bacterial translocation and renal tubular			
dysfunction following thermal injury	Change in urine protein: creatinine and urine albumin: creatinine ratios		
To assess the impact of thermal injury and intestinal permeability on the intestinal microbiome compared			

Objectives	Endpoints		
to healthy participants	convalescent stool samples		
To assess the impact of pre-existing co-morbid conditions on intestinal permeability and clinical outcome following thermal injury	Medical history and drug history at the time of admission		
To assess wound healing	Time to wound recovery (e.g. 95%)		
To characterise parameters that may influence drug PK/PD	Determine fluid input/output balance over time		
	Changes in serum albumin and plasma creatinine		
To characterise intestinal microbiota, and correlate its composition with both intestinal permeability and bacterial detection in blood	 Changes in intestinal microbiome Bacterial markers of translocation 		

1.2.2. Final Reporting Objectives & Endpoints Following Study Termination

	jectives	Endpoints			
Pri	mary Objectives	Primary Endpoints			
•	To determine the impact of thermal injury on the magnitude of small intestinal permeability change as soon as possible following injury compared to healthy participants	Lactulose/Mannitol (L/M) ratio at entry			
•	To characterise the effect of thermal injury on small intestinal permeability over time and establish the clinical and demographic factors which can influence it	Changes in L/M ratio over time			
Ex	ploratory Objectives	Exploratory Endpoints			
•	To determine the impact of thermal injury on colonic permeability as soon as possible following injury compared to healthy participants	Fractional excretion of sucralose at entry			
•	To characterise the effect of thermal injury on colonic permeability over time	Changes in the fractional excretion of sucralose over time			
•	To assess plasma and urine biomarkers of intestinal permeability and bacterial translocation	Change in markers of intestinal mucosal damage samples from blood			
		Change in bacterial markers of translocation			
•	To assess the impact of pre-existing co-morbid conditions on intestinal permeability and clinical outcome following thermal injury	Medical history and drug history at the time of admission			

1.3. Study Design

Note: The above design was prior to study termination. The study was terminated before any subjects had reached day 28. Hence, later visits are not included in the analysis.

1.4. Statistical Hypotheses / Statistical Analyses

- No formal hypothesis testing is planned.
- The key factors of interest in this study were to understand (i) the nature of any differences at entry in intestinal permeability between healthy participants and thermal injury participants (ii) to understand the trajectory of changes in intestinal permeability over time.

2. PLANNED ANALYSES

2.1. Interim Analyses

No formal interim analysis will be performed.

2.2. Final Analyses

The analyses will be performed after completion of the following sequential steps:

- 1. All subjects have completed Day 28 assessments or have withdrawn from the study.
- 2. All required database cleaning activities have been completed and final database release and database freeze has been declared by Data Management.
- 3. All protocol deviations have been confirmed.
- 4. Analysis population exclusions have been confirmed.
- 5. Database freeze has been declared by Data Management.

3. ANALYSIS POPULATIONS

Population	Definition / Criteria	Analyses Evaluated
Screened	All participants who were screened for eligibility	Study PopulationAll Listings
Safety	Comprise of all participants who receive at least one dose of STM and have at least one post-dose safety assessment.	Safety
Evaluable	Comprises of all participants in the safety population excluding any healthy volunteers that received any concomitant medication or food and drink containing STM (lactulose, mannitol and sucralose), as identified by review of the protocol deviations.	EfficacyBiomarkerStudy Population

NOTES:

 Please refer to Appendix 8: List of Data Displays which details the population to be used for each display being generated.

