8.2.1. Other Withdrawal Criteria

- A participant will be withdrawn from the study following positive (and confirmed) HIV test at screening; Serologic evidence of active Hepatitis B (HB) infection based on the results of testing for HBsAg, and anti-HBc or a positive test for Hepatitis C antibody confirmed by Hepatitis C RNA or antigen testing. If HCV RNA is not available, then the positive test for Hepatitis C antibody alone would be exclusionary. Results must be discussed with the medical monitor to withdraw the participant from the study and commence therapy according to local practice.
- Healthy participants that are treated with antibiotics during the duration of the study.
- Participants that experience signs and symptoms of gastro-intestinal infections during the duration of the study.
- Withdrawals related to mental capacity as described in Section 6 and [Appendix 3](#).
- Participants that received haemodialysis during the first 48 hours of the study (i.e. during the first measurement of intestinal permeability) will be excluded from the evaluable population and a replacement will be recruited.
- Participants that received haemodialysis during later time points will not be excluded, but consideration will be given to recruiting an additional participant if 3 or more intestinal permeability measurements occur concurrently with haemodialysis.

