10.4. Populations for Analyses

The **Safety Population** will consist of all subjects who receive at least 1 dose of STM and have at least on post-dose safety assessment.

The **Evaluable Population** will consist of all subjects who are entered into the study and have evaluable L/M ratio measurements.

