3.1. Protocol Deviations

Important protocol deviations (including deviations related to study inclusion/exclusion criteria, conduct of the trial, patient management or patient assessment) will be summarised and listed.

Protocol deviations will be tracked by the study team throughout the conduct of the study in accordance with the Protocol Deviation Management Plan.

- Data will be reviewed prior to freezing the database to ensure all important deviations and deviations which may lead to exclusion from the analysis are captured and categorised on the protocol deviations dataset.
- This dataset will be the basis for the summaries and listings of protocol deviations.

A separate listing of all inclusion/exclusion criteria deviations will also be provided. This summary will be based on data as recorded on the inclusion/exclusion page of the eCRF.

Prospective approval of protocol deviations to recruitment and enrolment criteria, also known as protocol waivers or exemptions, is not permitted.

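### The SAP's Evaluable population omits, without declaring it, the protocol's exclusion of participants haemodialysed in the first 48 hours

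*SAP*

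**What the plan says.** Protocol 8.2.1 (Amendment 2, the version the SAP cites) has two rules on dialysis.

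- Early dialysis: "Participants that received haemodialysis during the first 48 hours of the study", which it equates with the first permeability measurement, "will be excluded from the evaluable population and a replacement will be recruited".
- Later dialysis: "Participants that received haemodialysis during later time points will not be excluded".

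Protocol 10.4 defines the Evaluable Population as "all subjects who are entered into the study and have evaluable L/M ratio measurements".

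SAP 3 defines Evaluable as follows: "Comprises of all participants in the safety population excluding any healthy volunteers that received any concomitant medication or food and drink containing STM". The SAP's Safety population needs one dose of the sugar test material and one safety assessment after it. SAP 6.1.3 bases the primary analyses on Evaluable.

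SAP 1.1 states: "Changes from the originally planned statistical analysis specified in the protocol (Dated:26SEP2017) are outlined in Table 1". Table 1 has rows for co-primary objective 1 and for exploratory objectives 1, 3, 4, 5, 7, 8 and 9. None concerns an analysis population.

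**The concern.** The protocol names the evaluable population and says who must be left out of it. The SAP redefines that population, leaves the rule out, and does not list the change where it says changes are listed. The population feeds the co-primary L/M summaries (Tables 2.1 to 2.3), the sucralose summaries (Tables 2.4 to 2.6) and the TI figures.

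The study stopped with three TI participants, so a single inclusion decision carries great weight. SAP 4.2 takes Day 1 as baseline. An early-dialysed participant tested on Day 1 would therefore carry that value into every change and % change figure of their own.

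**Working it through.** **1. The definitions side by side**

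| Condition | Protocol | SAP 3 | Declared in SAP Table 1? |
|---|---|---|---|
| Dialysed in first 48 hours: out | Yes (8.2.1) | Absent | No |
| Evaluable L/M measurements needed | Yes (10.4) | Absent | No |
| Healthy volunteers exposed to the test sugars: out | No population rule | Added | No |
| Dialysed later: stay in | Yes (8.2.1) | Stay in | Not needed |

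**2. Does anything else in the SAP restore the early-dialysis rule?**

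- SAP 2.2, step 4, requires only that "Analysis population exclusions have been confirmed". It gives no criterion.
- SAP 3.1 has data reviewed so that "deviations which may lead to exclusion from the analysis are captured and categorised on the protocol deviations dataset". Neither document classes dialysis as a protocol deviation. Protocol Table 3 lists renal replacement therapy as an expected complication of severe burns.
- SAP 10.6.1 keeps the available planned data of withdrawn participants in tables and figures. Placing the rule under withdrawal criteria therefore does not remove the data.
- Early termination ends the replacement half of the protocol rule. The exclusion half does not depend on replacement.

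So nothing restores it.

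**3. Weight of one participant**

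The only figures the plan gives that bear on this point are the TI numbers in SAP 1.1: 25 planned, 3 achieved. The weight of one person in an arithmetic mean is 1/n.

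- Planned: 1/25 = 4%.
- Achieved: 1/3 = 33%.

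**4. TI numbers if the rule is restored**

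Let m be the number of TI participants dialysed in the first 48 hours. The documents do not give m, so its range is 0 to 3. The TI Evaluable n is 3 − m, that is 3, 2, 1 or 0. For m = 1 at the same SD, the standard error changes by (SD/√2)/(SD/√3) = √(3/2) = 1.22.

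**5. Displays affected by a population-wide exclusion (SAP Appendix 8)**

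- Tables on Evaluable: 1.1 and 1.5 to 1.8 (5), 2.1 to 2.6 (6), 4.1 to 4.6 (6). Total 5 + 6 + 6 = 17.
- Figures on Evaluable with TI data: 2.2, 2.3 and 2.5 to 2.8 (6), 4.1 to 4.4 (4). Total 6 + 4 = 10.

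**6. The missing L/M condition**

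A person with no L/M result adds nothing to an L/M mean, and the table shell shows N and n separately. In the L/M tables this omission changes N and not the estimate. It also bears on who is counted in the study population tables.

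**The case against.** The best case for the plan is that the gap may be empty. The SAP was written after termination, with three TI participants known, and its authors may have known that none was dialysed early. The analysis is purely descriptive. Figures 2.2 and 2.3 and Listing 24 show individual values. SAP 7.1 enters protocol Table 3 complications as disease-related events, so renal replacement therapy should appear in Table 3.3 and Listing 17.

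Much of this stands and it limits the harm. It does not restore the exclusion. The mean and SD tables are the reported co-primary summary, and Listing 7 (subjects excluded from a population) would not name a person whom the SAP definition keeps. What the authors knew is not in the documents.

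Some stronger readings are tempting and are not supported:

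- *A dialysed participant has distorted the results.* The documents do not say that any TI participant was dialysed in the first 48 hours.
- *The size or direction of a dialysis effect on L/M is known.* The amendment history says only that dialysis may filter out lactulose and mannitol. If both were cleared equally, the ratio would not change.
- *The baseline would always be affected.* The schedule of activities allows a first test on Day 2, and SAP 4.2 then sets baseline to missing, so there are no change values to distort.
- *Excluding only sugar-exposed healthy volunteers breaches the protocol.* Protocol 6.6.1 asks for documentation and for the test to stop, and sets no population exclusion for either group. The SAP's rule is a new asymmetry that needs declaring.
- *Keeping later-dialysed participants is an error.* Protocol 8.2.1 says they stay.

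**Conclusion.** The point holds as a mismatch between protocol and SAP that should be fixed. A TI participant dialysed in the first 48 hours would stay in Evaluable under the SAP and is excluded under the protocol. The consequence is conditional on that person being in the Safety population with a calculable L/M ratio. They would then be one of at most three, or 33% of the TI mean if all three contribute. The baseline consequence further requires a Day 1 test.

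No figure can be put on the bias. If the record check finds nobody affected, the numerical results stand and what remains is an undeclared change to the primary population, which is minor. The loss of the evaluable-L/M condition is a lesser part of the same point.

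**What to change.** 1. In SAP 3, put back into the Evaluable definition the first-48-hour haemodialysis exclusion of Protocol 8.2.1 and the evaluable-L/M condition of Protocol 10.4. Apply them to the whole population, as the protocol does. Limiting the exclusion to the L/M and sucralose displays would create another population that the protocol does not have.
2. Add a row to SAP Table 1 declaring and justifying any population change that remains, including the new exclusion of sugar-exposed healthy volunteers.
3. Keep participants dialysed later in Evaluable, as Protocol 8.2.1 states.
4. Check the three TI records for dialysis in the first 48 hours and report how many were affected, including if none.

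The cost is a few lines of SAP text, one table row and three record checks. Dialysis timing may need the clinical notes, since Protocol 9.5.3 draws its haemofiltration data from notes review. The downside is that one exclusion takes TI n from 3 to 2 across 17 tables and 10 figures, with a standard error 1.22 times larger at the same SD. The excluded person's values stay visible in the Screened-population listings, including Listings 24 and 25.

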5.4.3. Inclusion of Healthy Participants

Patient facing material (i.e. poster) will be used to facilitate recruitment of the healthy participants. Healthy participants will be recruited to this study to provide a baseline for endpoint measures on intestinal permeability and the gut microbiome.

Three measurements of intestinal permeability are required in order to define an average given the variability in healthy participants reported previously. The timing of the replicates follows the intense time course of the study to control for day-to-day variation over a 15 day period.

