6.6. Lifestyle Restrictions

6.6.1. Meals and Dietary Restrictions

- Participants will be fasted (or feed stopped) for **3 hours** prior to STM administration and for **3-5 hours** afterwards. For thermally injured participants these fasts should be aligned with those required for routine clinical care (feed holds, before surgical interventions) where possible.
- Refrain from consumption of the following for **24 hours** before and after the administration of STM:
 - Foods/drinks/medicines and other products which contain sucralose, lactulose or mannitol as artificial sweeteners.

N.B. If cannot be avoided, then clear documentation of its administration is required and the current test to stop. If urine samples have been collected PRIOR to administration of the drug, then these can still be sent for analysis

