6.1.3. Population of Interest

The primary analyses will be based on the evaluable population, unless otherwise specified.

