8.1.3. Population of Interest

The exploratory efficacy analyses will be based on the evaluable population, unless otherwise specified.

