10.8.8. Biomarker Tables

Pharma	codynamic and	Biomarker: Tables			
No.	Population	IDSL / Example Shell	Title	Programming Notes	Deliverable [Priority]
Intestin	al Permeability				
4.1	Evaluable	PD_T1	Summary of Markers of Intestinal Mucosal Damage	Note: Absolute Values Summary by: Study group and Visit	SAC
4.2	Evaluable	PD_T1	Summary of Change in Markers of Intestinal Mucosal Damage	Note: CFB Values Summary by: Study group and Visit	SAC
4.3	Evaluable	PD_T1	Summary of % Change in Markers of Intestinal Mucosal Damage	Note: %CFB Values Summary by: Study group and Visit	SAC
Bacteria	al Translocation				
4.4	Evaluable	PD_T1	Summary of Bacterial Markers of Translocation	Note: Absolute value Summary by: Study group and Visit	SAC
4.5	Evaluable	PD_T1	Summary of Change in Bacterial Markers of Translocation	Note: CFB Values Summary by: Study group and Visit	SAC
4.6	Evaluable	PD_T1	Summary of % Change in Bacterial Markers of Translocation	Note: %CFB Values Summary by: Study group and Visit	SAC

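### SAP section 3 drops a healthy participant from every L/M, sucralose and biomarker summary for one test-sugar exposure that the protocol treats as a fault of a single test, and does not declare the change

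*SAP*

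**What the plan says.** SAP section 3 defines the Evaluable population as the Safety population "excluding any healthy volunteers that received any concomitant medication or food and drink containing STM (lactulose, mannitol and sucralose", with exposures identified from the review of protocol deviations. The unit removed is the participant. There is no per-visit or per-test version, and the exclusion applies to the healthy group only.

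That population governs nearly all summaries. SAP 6.1.3 says "The primary analyses will be based on the evaluable population, unless otherwise specified", and SAP 8.1.3, on biomarkers, says "The exploratory efficacy analyses will be based on the evaluable population, unless otherwise specified". SAP Appendix 8 assigns it to Tables 2.1-2.6 and Figures 2.1-2.8 (L/M and sucralose) and to Tables 4.1-4.6 and Figures 4.1-4.4 (biomarkers), starting with "Summary of Markers of Intestinal Mucosal Damage". Listings 24 and 25 use the Screened population.

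Protocol 6.6.1 restricts the three sugars for 24 hours either side of each dose of sugar test material. Where this fails, it says: "If cannot be avoided, then clear documentation of its administration is required and the current test to stop". It adds: "If urine samples have been collected PRIOR to administration of the drug, then these can still be sent for analysis". Protocol 8.2.1 does not make such exposure a reason for withdrawal. In protocol 10.4 the Evaluable population "will consist of all subjects who are entered into the study and have evaluable L/M ratio measurements", with no exposure exclusion. SAP Table 1, which sets out the changes from the protocol analysis, does not mention the new definition.

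**The concern.** The two documents handle one event at different levels. The protocol loses a test, or the part of it after the exposure. The SAP loses the person. A healthy volunteer who takes a sucralose drink on the eve of the Day 15 test would lose the Day 1 and Day 8 tests as well, together with the single blood draw for biomarkers.

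This matters because the healthy group supplies the reference against which the burn profiles are read. Protocol 5.4.3 explains the replicate design: "Three measurements of intestinal permeability are required in order to define an average given the variability in healthy participants reported previously". Discarding clean replicates works against that purpose. With 3 thermally injured participants and no formal comparison planned, the individual plots against a healthy line carry much of the interpretation.

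**Working it through.** **1. Are the other tests clean by the protocol's own window?** Healthy visits are on Days 1, 8 and 15, each ±1 day (protocol 2.1). The smallest gap between neighbouring visits is 7 - 2 = 5 days, against a restriction of 24 hours before and after dosing. An exposure that breaches the window of one test lies outside the windows of the other two.

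**2. Does the rest of the SAP need whole-person exclusion?** No. SAP 10.5.2 takes the healthy average over whatever data each participant has, so a missing test is already accommodated. It also derives fractional excretion separately for 0-5 h and 0-24 h, so an uncontaminated early collection can stand alone. SAP 10.6.1 keeps the available planned data of withdrawn participants in the summaries. A healthy volunteer withdrawn for antibiotics therefore keeps earlier tests, while one with a single sugar exposure keeps none.

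**3. Which displays lose their reference data?** Figures 2.2, 2.5 and 2.7 use the healthy average. Figures 4.1 and 4.3 use the healthy Day 1 average. For the percent-change Figures 2.3, 2.6 and 2.8, the notes in SAP Appendix 9 leave the line at zero or at the healthy average, to be decided on the data. Figures 4.2 and 4.4 have a line at zero and are unaffected in that respect.

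**4. Which biomarkers?** iFABP, citrulline, zonulin, occludin and sCD14 are not test sugars. That a dietary sugar exposure leaves them usable is an inference, since the documents do not say so. The microbial metabolites in SAP Table 4 come from urine (protocol Appendix 5), so the point is less clear for them.

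**5. The plan's own figure.** Protocol 10.2 gives 89% power for a 3-fold difference with 25 and 15 participants, log SD 1.15 and two-sided 0.10. A two-sample noncentral t with 38 df gives 0.890, so the figure reproduces. It does not measure this issue, because the SAP plans no test.

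**6. Size.** Inputs: 15 planned healthy participants (protocol 5.2) and 3 tests each. The number exposed, k, is not given; one affected test per exposed person is assumed.

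- Tests kept under the SAP rule: 3 × (15 - k) = 45 - 3k.
- Tests kept under test-level exclusion: 45 - k.
- Clean tests lost: the difference, 2k, plus k sets of Day 1 blood markers.

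For the L/M mean, let r be the within-person correlation (assumed 0.2 to 0.8). The variance of a participant's average, in units of SD², is v3 = r + (1 - r)/3 from three tests and v2 = r + (1 - r)/2 from two. Taking the reference as the mean of participant averages:

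- SE under the SAP rule = SD × √(v3/(15 - k))
- SE at test level = SD × √((15 - k)v3 + k·v2)/15

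The SD cancels in the ratio. Example with r = 0.2, k = 3: v3 = 0.4667 and v2 = 0.6. With SD 1.15 the SEs are 0.2268 and 0.2086, a ratio of 1.087.

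For Day 1 blood markers, test-level exclusion loses nobody, so the ratio is √(15/(15 - k)).

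| k | Tests kept, SAP rule | Tests kept, test level | L/M SE ratio | Blood-marker SE increase |
|---|---|---|---|---|
| 1 | 42 | 44 | about 1.03 | 3.5% |
| 3 | 36 | 42 | 1.09-1.11 | 11.8% |
| 5 | 30 | 40 | 1.17-1.22 | 22.5% |

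**The case against.** The best defence is that a strict participant-level exclusion is a recognised, conservative way to keep a reference group clean. Protocol 6.6.1 governs conduct, not analysis populations: permission to send urine for assay is not a promise to analyse it. Protocol 10.4 is itself worded by subject and leaves evaluable measurements undefined, and protocol section 10 defers detail to the analysis plan. Exclusions also come only from reviewed deviations and are confirmed before analysis (SAP 2.2 and 3.1), so ordinary sweetener use outside the 24-hour window should not count. Finally, with 3 burn participants and no formal analysis, a few percent of standard error changes no planned inference.

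Much of this stands. The sponsor may choose a stricter population, and the effect may be small or nil. It does not explain why tests that the protocol's own window treats as clean should go, why blood markers should go with them, or why the change is absent from SAP Table 1.

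A reader might infer more than the documents support on three points:

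- **Data vanish from every output.** They do not; Listings 24 and 25 retain them.
- **Every burn profile depends on the healthy line.** Some percent-change figures use zero, or may use it.
- **Evaluability should be set sugar by sugar, keeping L/M when only sucralose was taken.** SAP 10.5.2 computes L/M from lactulose and mannitol alone, but protocol 6.6.1 stops the test for any of the three sugars. Nothing in the documents establishes that sucralose exposure leaves the other two results intact.

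**Conclusion.** The inconsistency is real and should be corrected. SAP section 3 applies a stricter, undeclared, person-level rule to an event that the protocol confines to one test. Healthy data with no stated fault therefore leave the reference.

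The size is conditional on k and on 15 participants being enrolled as planned. The L/M figures also assume the correlation range and that the affected test yields nothing usable. At k = 1 the avoidable loss in L/M precision is about 3%; at k = 5, which would mean one third of the volunteers, it is 17% to 22%. At k = 0 nothing changes. Comparing the SAP rule with a fully clean sample of 15 would overstate the L/M loss, because test-level exclusion also gives up k tests; that comparison is right only for the Day 1 blood markers.

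A reader might also infer a biased reference or a loss of power. The documents show no direction of bias, and no formal test is planned. What is at stake is the precision of a descriptive reference.

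**What to change.** In SAP section 3:

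- Keep exposed healthy participants in the Evaluable population.
- Set to missing only the sugar results of the affected test (L/M ratio and fractional excretion of sucralose), retaining a 0-5 h result where that urine was collected before the exposure.
- State that the exposure rule does not apply to blood biomarkers.
- Add the population definition, with its reason, to SAP Table 1.

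The cost is revised wording and a test-level flag, which can be set during the deviation review that SAP 3.1 already requires before the database is frozen. No new data are needed. The drawback is that healthy participants will contribute unequal numbers of tests, so the number of tests behind each average should be reported.
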